Important progress has been made in the control of malaria in pregnancy in Africa with the introduction of intermittent preventive treatment in pregnancy (IPTp). The WHO recommends the administration of IPTp with sulfadoxine-pyrimethamine (SP) during antenatal visits in high malaria transmission areas of sub-Saharan Africa.⁶ However, SP resistance has become widespread especially in East and Southern Africa, greatly limiting the protective effect of IPTp with SP. The development of safe, efficacious and affordable replacement of SP for IPTp is an urgent priority.

The combination of azithromycin (AZ) and chloroquine (CQ) could potentially replace SP for IPTp. AZ and CQ are synergistic in vitro and in vivo against CQ resistant strains of *P. falciparum*. Co-administration of AZ and CQ has demonstrated efficacy, safety and tolerability in two multi-country Phase 3 clinical studies (A0661134 and A0661155) in the treatment of symptomatic uncomplicated malaria in non-pregnant adults in sub-Saharan Africa. AZ and CQ have been on the market for several years and have extensive safety records in adults, children and pregnant women. Both AZ and CQ have been widely used in all trimesters of pregnancy and are considered safe in pregnant women as individual agents. In high-income countries, AZ is commonly used to treat and prevent sexually transmitted infections (STIs) including *Neisseria gonorrhoeae* and *Chlamydia trachomatis* infections. In sub-Saharan Africa, two randomized controlled clinical trials.^{21, 22} found that a single dose of 1000 mg AZ was comparable to benzathine penicillin G in curing syphilis. The incidence of adverse fetal outcomes has been shown to be reduced by about 30% when these three STIs were treated in pregnancy.²³ In addition, AZ has also demonstrated protective effect against *Trichomonas vaginalis* when used as chemoprophylaxis²⁴ and reduced the risk of preterm delivery attributable to *T. vaginalis*, even in the second trimester when first-line treatment, metronidazole, should be avoided.²⁵

A fixed dose combination tablet formulation of AZ and CQ (AZCQ, 250 mg AZ/155 mg CQ base) has been developed specifically for the IPTp indication and will be evaluated in IPTp studies. In a clinical pharmacology study A0661186, AZCQ administration resulted in the systemic exposures to AZ, CQ and des-ethyl CQ (an active metabolite of CQ) at levels comparable to those achieved following administration of commercial standalone tablets of AZ (Zithromax) and CQ (Aralen) evaluated in adult treatment studies.

A Phase 3 randomized controlled clinical study to demonstrate the superiority of AZCQ IPTp regimen over SP IPTp regimen is planned in East and Southern sub-Saharan Africa where SP resistance is emerging as an issue and where SP is the current standard of care for IPTp. This will be the pivotal study for regulatory submissions to European Medicines Agency (EMA) and to the national regulatory agencies in Sub-Saharan African countries.

AZCQ is expected to exert IPTp effect through multiple mechanisms including peripheral parasitological clearance in pregnant women, prevention of re-infections, prevention/treatment of placental malaria and prevention/treatment of STIs. The relative contributions of these mechanisms towards IPTp effect are not yet known. The study A0661201 is an open label, non-comparative parasitological clearance study of a single 3-day treatment course of AZCQ in about 166 pregnant women in second and third trimesters of pregnancy with asymptomatic parasitemia. This study will help to characterize the magnitude of parasitological clearance required for the IPTp effect observed in A0661158 study, and will serve as a supportive study in IPTp regulatory dossier. A0661201 study will also evaluate pharmacokinetic (PK) exposures, of both AZ and CQ in pregnant women following administration of a single 3-day treatment course of AZCQ. Subjects will be followed up to Day 42 after the first dose, and followed through delivery or to pregnancy termination for safety assessments of Exposure in Utero (EIU).

Objectives

The primary objective is to evaluate the peripheral parasitological clearance rate of AZCQ on Day 28 polymerase chain-reaction (PCR) corrected following the first dose of 3-day dosing regimen of AZCQ in asymptomatic pregnant women with *P. falciparum* parasitemia.

Secondary objectives include the evaluation of:

1. Parasitological clearance rates (PCR corrected) at Days 7, 14, 21, 35, and 42 post first dose of study medication;
2. Parasitological clearance rates (PCR uncorrected) at Days 7, 14, 21, 28, 35, and 42 post first dose of study medication;
3. Pharmacokinetic exposure of AZCQ;
4. Safety and tolerability of AZCQ.

Study Design

This is a Phase 3, open label, single arm non-comparative out-patient study in pregnant women during their second and third trimesters of pregnancy. Women will be screened for peripheral parasitaemia. Women who are screened but not included in the study (screen failures) will be referred to their doctors and will be given standard antenatal care (ANC) including IPTp. Subjects with asymptomatic parasitemia (counts of 80 -100,000/ μ L) will receive a single 3-day course of AZCQ IPTp regimen. They will be followed up on a weekly basis up to Day 42, and following delivery or at termination of pregnancy for EIU safety assessments. After completing Day 42 evaluation, all subjects will continue to receive standard antenatal care including IPTp with SP if the gestational age allows additional IPTp course(s). The peripheral parasitological response will be evaluated on Days 7, 14, 21, 28, 35 and 42. Pharmacokinetics evaluation will be conducted on blood samples collected from the subjects who consented for such test. Systemic concentrations of AZ, CQ and desethyl-CQ (active metabolite of CQ) will be evaluated on Day 0 predose, Day 2 predose, 2 hours (as close to 2 hours as possible) and 8 hours (window: 4 to 12 hours) post dose, and at a random time point on Days 7 and 14. In addition, due to the long half-life of CQ, systemic concentrations of CQ and desethyl-CQ will also be measured at a random time point on Days 21 and 28. All subjects will be followed up for pregnancy outcomes as a safety endpoint. Long lasting insecticidal-treated bednets (LLITs) will be given to all subjects on Day 0 of the study with the instructions to use them; installation of LLINs will be verified during the Day 1 home visit by fieldworker(s).

Study Treatment

Study drug is a fixed dose tablet of AZCQ containing 250 mg AZ and 155 mg CQ base. All subjects will be administered a single 3-day course of AZCQ IPTp regimen: a single dose of 1000 mg AZ/620 mg CQ base (4 fixed dose combination tablets of AZCQ: 250mg/155mg) administered *per os* (PO, orally) once daily for 3 days (Days 0, 1, 2). The first dose (on Day 0) and the third dose (on Day 2) will be administered under supervision by investigators at the antenatal care (ANC) facility, and the second dose on Day 1 will be administered under supervision by a field worker at home.

Main Endpoints

Primary Efficacy Endpoint

- Parasitological response (PCR corrected) at Day 28 post first dose of study medication.

Secondary Parasitological Clearance Endpoints

- Parasitological responses (PCR corrected) at Days 7, 14, 21, 35, and 42 post first dose of study medication;
- Parasitological responses (PCR uncorrected) at Days 7, 14, 21, 28, 35, and 42 post first dose of study medication;

- Parasite counts at each visit – number of asexual *P. falciparum* parasites per microliter of blood.

Pharmacokinetic Evaluation

- Pharmacokinetic exposure of AZCQ.

Safety Endpoints

- Safety and tolerability endpoints include spontaneously reported adverse events, temperature, hemoglobin concentrations, and the EIU safety assessment.

Statistical Methods

This study is designed to estimate the incidence for the primary endpoint. No statistical hypothesis will be tested.

The proportion of subjects with parasitological response (PCR corrected) at Day 28 following the first dose of study medication will be estimated for the primary endpoint using the modified intent-to-treat (MITT) and per protocol (PP) subject populations. Similar analysis will also be performed for an intent-to-treat (ITT) population will also be defined. The proportion will be estimated from the Kaplan-Meier curve of the time to the first occurrence of parasitological failure (PCR corrected). Use of the Kaplan-Meier curve/product limit estimator is recommended by WHO⁸ and has been used in analyzing primary efficacy endpoints in late stage antimalarial treatment clinical trials. See Section 9 for details.

An early analysis of the data will be performed on parasitological clearance endpoints including the primary endpoint, when all subjects complete Day 42 visit (ie, 42 days of follow-up post first dose), or withdraw from the study early.

[figure not shown]
Number of Subjects

Approximately 166 subjects will be enrolled in the study. Since this is a supportive study to understand one of the possible mechanisms for IPTp effect, it is not powered for formal hypothesis testing. The sample size will yield a half width of a 2-sided 95% confidence interval (CI) to be ≤ 5 percentage points with probability=0.80 for the primary efficacy endpoint, using a large sample normal approximation to the binomial, provided the true underlying incidence is $\geq 95\%$, and assuming approximately 10% will drop out.

Independent Data Monitoring Committee (IDMC)

The IDMC constituted for IPTp will review safety data at regular intervals to be determined at the time of DMC charter development.

Study Schematic

090177e1811d3ccb\Approved\Approved On: 19-Feb-2010 20:59

SCHEDULE OF ACTIVITIES

Protocol Activity	Treatment			Follow Up Visits						
	Day 0 ^a	Day 1	Day 2	Day 7	Day 14	Day 21	Day 28	Day 35	Day 42	At/Post Delivery ^b
Informed Consent Process	X									
Medical History	X									
Obstetrical History	X									
Concomitant Treatment History	X	X	X	X	X	X	X	X	X	X
Rapid Diagnostic Test (eg, Binax)	X									
Complete Physical Exam	X									
Limited Physical Exam									X	
Oral Temperature	X	X	X	X	X	X	X	X	X	
Routine Obstetric checkup	X									
Ultrasound ^c	X									
Laboratory										
Peripheral Blood Smears ^d	X			X ^d	X ^d	X ^d	X ^d	X ^d	X ^d	
Hemoglobin (Hb)	X								X	
Urine Pregnancy Test ^e	X									
Urine Test for Glucose & Protein	X									
Blood Blot for Molecular Testing										
Molecular Genotyping for P. Falciparum ^f	X			X ^f	X ^f	X ^f	X ^f	X ^f	X ^f	
Genetic Marker for CQ Resistance	X									
Administer Treatment Azithromycin-Chloroquine (AZCQ ^g)	X	X	X							
Distribute Long lasting insecticidal-treated bednets (LLITs)	X									
Confirm the Installation of LLINs at Home by Fieldworkers		X								
Blood Samples for AZ, CQ and desethyl-CQ Analysis ^h	X ⁱ		X ^j	X ^k	X ^k	X ^k	X ^k			
Adverse Events Assessment	X	X	X	X	X	X	X	X	X	
Exposure in Utero (EIU) Assessment ^l										X

090177e1811d3ccb\Approved\Approved On: 19-Feb-2010 20:59

- ^a All tasks should be performed prior to the first dose except AE assessment and bednet distribution.
- ^b All subjects should be followed up following delivery or at termination of pregnancy for EIU assessment. In case of no associated serious adverse events (SAE), the follow-up visit should take place within 14 calendar days after expected date of delivery or termination of pregnancy.
- ^c Ultrasound will be performed only if the urine pregnancy test is positive.
- ^d Peripheral blood smears (thick and thin) will be prepared at visits on Day 0 (predose) and weekly intervals afterwards. Two smears per subject at each time point.
- ^e If not done at any prior ANC visit for this pregnancy.
- ^f The blood blot will be collected at baseline (predose) and each visit through Day 42 but evaluated only if positive by the blood smear following initial clearance.
- ^g The first dose on Day 0 and the third dose on Day2 will be administered under supervision by investigator at the antenatal care (ANC) clinic, and the second dose on Day 1 will be administered at home under supervision of a field worker(s).
- ^h PK evaluation will be conducted on blood samples collected from the subjects who consented for such test. Insert intravenous catheter as deemed necessary. Subjects who received even one dose will be followed up for all subsequent PK sample collection. The exact date and time of blood sample collection will be recorded.
- ⁱ Two PK blood specimens (one for AZ and one for CQ and desethyl-CQ analyses) will be collected at predose.
- ^j Two PK blood specimens (one for AZ and one for CQ and desethyl-CQ analyses) will be collected at predose, 2 hours (as close to 2 hours as possible) and 8 hours (window: 4 to 12 hours) following dosing on Day 2.
- ^k Two PK blood specimens (one for AZ and one for CQ and desethyl-CQ analyses) will be collected at visits on Days 7 and 14 (a random time point), and only blood sample (for CQ and desethyl-CQ analyse) will be collected on Days 21 and 28 samples (a random time point).
- ^l EIU assessment: Every attempt should be made to follow up the subject following delivery or pregnancy termination. In case of no associated serious adverse events (SAE), subjects should be followed up by fieldworkers at clinic or at home within 14 calendar days after expected date of delivery or termination of pregnancy. EIU assessment includes maternal information, delivery and neonatal information. Fetal information will be collected in the event of pregnancy termination.

TABLE OF CONTENTS

1. INTRODUCTION	13
1.1. Indication	13
1.2. Background.....	13

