6. STUDY PROCEDURES

6.1. Study Period

6.1.1. Baseline/Day 0 Visit (at ANC clinic/center)

Baseline/Day 0 – Pre Assessment of Study Eligibility

After informed consent is obtained, the subject must have the following procedures performed prior to the start of therapy:

- Medical history;
- Obstetrical history;
- Urine pregnancy test (if not done at any prior ANC visit for this pregnancy);
- Concomitant treatment history;
- Rapid diagnostic test for *P. falciparum* (eg, Binax, See Appendix 1);

- Complete physical examination;
- Oral Temperature;
- Routine obstetric checkup;
- Obstetrical ultrasound (if urine pregnancy test positive);
- Thick and thin peripheral blood smears for parasite identification and counts (2 smears per subject) in subjects with Rapid Diagnostic Test positive for *P. falciparum*;
- Hemoglobin level (with HemoCue™);
- Urine analysis for glucose and proteins;
- A dried blood blot for molecular genotyping (reinfection vs. recrudescence, eg, MSP1/MSP2) of parasite and for genetic markers of CQ resistance (eg, PfCRT);
- Two predose blood samples (one for AZ and one for CQ and desethyl-CQ analyses) from the subjects who consented for PK analysis (See Section 7.3 Pharmacokinetic Assessments). The exact date and time of blood sample collection will be recorded.

Day 0 – Post Assessment of Eligibility

Subjects who have met all inclusion/exclusion requirements will have the following procedures performed:

- Administer treatment (AZCQ);
- Assess adverse events;
- Distribute LLINs.

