8.2. Reporting Period

For serious adverse events, the reporting period to Pfizer or its designated representative begins from the time that the subject provides informed consent, which is obtained prior to the subject's participation in the study, ie, prior to undergoing any study-related procedure and/or receiving investigational product, **through Day 42 and including 39 calendar days after the last administration of the investigational product, or until one month after the delivery or the termination of pregnancy (which ever is later)**. If pregnancy outcome meets the classification as a serious adverse event, it will be reported accordingly as serious adverse event (refer to Section 8.9 for details). Any serious adverse event occurring any time after the reporting period must be promptly reported if a causal relationship to investigational product is suspected.

Adverse events (serious and non-serious) should be recorded on the CRF from the time the subject has taken at least one dose of study treatment through last subject visit.

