9.3. Safety Analysis

Adverse events, history of concomitant treatments, hemoglobin, temperature, and the EIU safety assessment will be recorded for each subject during the study according to the schedule of assessments. Standard safety reporting tables will summarize and list the safety data.

Each adverse event will be counted once according to the date of onset. If the adverse event onset was prior to the first dose of study drug and the event does not increase in severity after initiation of study drug, the adverse event is then considered to be a pre-treatment adverse event and will not be counted in the treatment-emergent adverse event incidence tables. If the onset is prior to the first dose of study drug and the severity increases thereafter, the event is counted as a treatment-emergent adverse event. An adverse event with onset after the first dose of study drug will be counted as a treatment-emergent adverse event. This rule is consistent with the treatment-emergent signs and symptoms (TESS) convention for counting adverse events.

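### Adverse event collection starts only after the first dose, yet the treatment-emergent rule needs pre-dose onset and severity, and no graded symptom baseline is required

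*Protocol*

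**What the plan says.** **When AEs are assessed on Day 0.** Footnote a to the Schedule of Activities reads "All tasks should be performed prior to the first dose except AE assessment and bednet distribution". Section 6.1.1 has two lists for that visit. The pre-dose list contains medical, obstetrical and concomitant treatment history, physical examination, temperature, obstetric checkup, hemoglobin and urine analysis, but no AE or symptom assessment. The second list opens with "Subjects who have met all inclusion/exclusion requirements will have the following procedures performed" and contains treatment, then AE assessment, then bednet distribution.

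**When AEs are recorded.** Section 8.2: "Adverse events (serious and non-serious) should be recorded on the CRF from the time the subject has taken at least one dose". The same section says that the period for reporting serious events to the sponsor "begins from the time that the subject provides informed consent".

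**How AEs are counted.** Section 9.3: "Each adverse event will be counted once according to the date of onset". An event is set aside as pre-treatment under this condition: "If the adverse event onset was prior to the first dose of study drug and the event does not increase in severity" after study drug is started. It is counted as treatment-emergent under the complementary one: "If the onset is prior to the first dose of study drug and the severity increases thereafter".

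**How severity is graded.** Section 8.7 has one three-level scale. It applies if the AE form requires it, and it describes the maximum intensity of the event.

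**The concern.** The counting rule in section 9.3 needs two facts about any symptom already present at enrolment: that it began before the first dose, and how severe it was then compared with afterwards. The collection rules in footnote a, section 6.1.1 and section 8.2 open only once dosing has begun. The window for collecting the data thus leaves out part of what the analysis uses.

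This matters because safety and tolerability is a secondary objective (section 2.1) and the study has a single arm (section 3), so no concurrent group shows the background rate of symptoms. Section 1.5.2.3 describes the events seen with the combination as mostly mild and gastrointestinal. Exclusion criterion 3 removes women with malaria symptoms but not women with other mild complaints. An analysis plan written later cannot restore a pre-dose grade that was never taken.

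**Working it through.** No sample size, rate or error level enters this point, and the protocol states no figure to reproduce. The check sets the counting rule against the data that the protocol requires.

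**Step 1. What section 9.3 needs, and where it is collected.**

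| Needed by section 9.3 | Required collection | Result |
|---|---|---|
| Onset before or after first dose | Onset date on the AE page, completed after dosing (8.2) | Available if the woman is asked and recalls it. For a symptom starting on Day 0, a date alone does not place it before or after dosing |
| Severity before first dose | None stated. The history and examination in 6.1.1 are not said to be graded | Not required |
| Severity after first dose | Maximum intensity, if the AE form asks for it (8.7) | Available if the form asks for it |

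**Step 2. Apply the rule to three women.** Suppose each reports nausea after dosing, and onset dates are correct.

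| Woman | Before dose | After dose | Class under 9.3 | What the AE page holds |
|---|---|---|---|---|
| A | none | moderate | emergent | onset after dose, maximum moderate |
| B | mild | moderate | emergent | onset before dose, maximum moderate |
| C | moderate | moderate | pre-treatment | onset before dose, maximum moderate |

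A is classified correctly. B and C have identical records but belong in different classes. It makes no difference whether the maximum covers the whole episode or only the time since dosing: both women read moderate either way. They can be separated only if someone noted B's milder state before dosing, which no section requires.

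**Step 3. Direction of the error.**
- If every event with pre-dose onset is set aside, B is lost and the incidence is too low.
- If events with unclear worsening are counted, C is included and the incidence is too high.
- If the pre-dose onset is not elicited, or a Day 0 onset is taken as post-dose, C looks like A and the incidence is too high.

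The text does not determine which of these would dominate.

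**Step 4. Serious events.** Section 8.2 opens sponsor reporting at consent and opens CRF recording, expressly including serious events, at the first dose. Section 8.12.2 says that all AEs go on the AE page and that the AE page and the separate serious-event form must agree where they hold the same data. A serious event between consent and dosing would have a sponsor form but, on the wording of section 8.2, no AE page entry to agree with.

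**The case against.** The strongest reply is that the protocol does collect a pre-dose baseline. The section 6.1.1 procedures precede treatment, and section 5.5 puts medications in use at study entry on the CRF. Section 9.3 works on the date of onset rather than the date of assessment, and nothing forbids a pre-dose onset date on an event written down after dosing. Section 8.11 has every subject questioned about AEs. The CRF is not shown and might grade history items.

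Much of this stands, and it rules out several stronger readings:

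- **That there is no baseline at all.** A reader might infer this, but it is wrong. What is missing is a requirement to grade ongoing symptoms before dosing. A pre-dose onset date helps with the first half of the section 9.3 rule. It does not help with the second half, which compares severity.
- **That background symptoms will be counted as drug effects.** Treatment-emergent does not mean drug-related. Section 8.8 requires a separate causality assessment for every AE.
- **That the incidence is inflated.** Step 3 shows errors in both directions.
- **That the number of affected women can be stated.** One might assume that 5 to 20% of women have a symptom on Day 0, giving 0.05 × 166 = 8.3 to 0.20 × 166 = 33.2 women, and compare this with the 7% diarrhoea in section 1.3.2.3 (0.07 × 166 = 11.6). The assumed prevalence has no source in the protocol. The 7% belongs to a 1,000 mg oral dose of azithromycin, not to a three-day combination course. Only women with the same symptom after dosing and an uninformative history would be affected. At the low end the comparison also reverses, since 8.3 is below 11.6.

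The serious-event mismatch is narrow too. The event still reaches the sponsor. The schedule puts consent and first dose on the same day, and exclusion criterion 5 bars conditions requiring hospitalization at presentation, so few such events should arise among treated women.

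**Conclusion.** The point holds as a mismatch between the collection window and the counting rule. Footnote a, section 6.1.1 and section 8.2 begin AE assessment and CRF recording after the first dose. Section 9.3 classifies by pre-dose onset and by change in severity. No section requires a pre-dose grade, and section 8.7 provides a single maximum. Worsened and unchanged pre-existing symptoms may therefore not be separable.

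The consequence is a risk of misclassification in the descriptive treatment-emergent tables, in either direction and of a size that the protocol does not allow one to estimate. The Day 28 parasitological estimate is untouched. The serious-event gap in section 8.2 is a smaller inconsistency of the same origin.

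This rests on the protocol text alone. If the CRF already takes the severity of ongoing symptoms before dosing, the practical risk largely disappears and only the wording needs aligning. It is a cheap improvement worth making.

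**What to change.** - **Section 8.2:** record AEs, serious and non-serious, on the CRF from informed consent, so that the start matches the serious-event reporting period.
- **Footnote a and section 6.1.1:** add to the pre-dose list a check of ongoing symptoms, with onset and severity grade on the section 8.7 scale. Keep the post-dose AE assessment, so that Day 0 has one before and one after the first dose.
- **CRF:** confirm that the AE page asks for severity, which section 8.7 leaves conditional, and that a Day 0 onset can be marked as before or after dosing.

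Section 9.3 can then be applied as written: the pre-dose grade is compared with the maximum after dosing. The cost is one extra Day 0 CRF item and some additional pre-treatment AE records to enter and clean. No visit is added, because history and examination already precede dosing on that day.
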